## 17.1. SERUM AND URINE CONCENTRATION DATA

### 17.1.1. BLOOD SAMPLE FOR SERUM PK ASSESSMENT

Blood must be collected from all subjects at the time points indicated below.

Day No.	Time Relative to Oral Lurasidone Dosing
-7	Predose and 2 hours postdose
-6	Predose and 2 hours postdose
Day No.	Timepoint Relative to Lurasidone or Placebo Injection Dosing
1	Predose and 2, 4, 6, and 12 hours postdose
2	24 hours post-injection dose
3	48 hours post-injection dose
4	72 hours post-injection dose
5	96 hours post-injection dose
6	120 hours post-injection dose
7	144 hours post-injection dose
15	336 hours post-injection dose
22	504 hours post-injection dose
29	672 hours post-injection dose
61	1440 hours post-injection dose

### 17.1.2. URINE SAMPLE FOR PK ASSESSMENT

Urine samples will be collected from all subjects at the time points indicated below.

Day No.	Time Interval Relative to Lurasidone or Placebo Injection Dosing
1	Predose -0.5 to 0 hour
1/2	0 to 24 hours post-injection dose
2/3	24 to 48 hours post-injection dose
3/4	48 to 72 hours post-injection dose
4/5	72 to 96 hours post-injection dose

---

Document:

Author:

Version Number:  
Version Date:

Final Draft  
11APR2019

Template No: CS\_TP\_BS016 Revision 4  
Effective Date: 01Apr2016

Reference: CS\_WI\_BS005

---

5/6	96 to 120 hours post-injection dose
6/7	120 to 144 hours post-injection dose.

### **17.1.3. SERUM AND URINE CONCENTRATION DATA ANALYSES**

Listings of PK blood and urine sample collection times as well as derived sampling time deviations will be provided. Concentrations of lurasidone and metabolites in serum and urine will be listed and serum concentrations will be summarized by analyte, dose level, and time point.

Any serum or urine lurasidone and metabolite concentrations in listings and/or summary statistics which are below the limit of quantification will be represented as "BLQ" in listings and/or tables. If the calculated mean concentration is BLQ, the mean shall be reported as BLQ and the SD, CV%, geometric mean, and GCV% shall be reported as ND (not determined). Geometric mean and GCV% rules for BLQ only apply for reporting of  $C_{max}$ . Minimum, median, and maximum may be reported and, if any are BLQ, they shall be reported as such and indicated as BLQ. Concentrations from serum and urine samples analyzed for the subset of subjects who receive placebo, if any, will be provided in a listing.

Graphical displays of individual subject and mean (+SD) serum lurasidone and metabolite concentrations will be presented on both linear and semi-logarithmic scales by time point including pre-dose.

## **17.2. PHARMACOKINETIC PARAMETERS**

For the noncompartmental analysis of serum lurasidone and metabolite (ID-14283, ID-14326, ID-11614, ID-20219, and ID-20220) concentration data, BLQ values will be considered 0 prior to  $t_{max}$ , missing between  $t_{max}$  and  $t_{last}$ , and 0 after  $t_{last}$ . For PK parameter calculations, predose samples that are BLQ or missing will be assigned a numerical value of zero. Any quantifiable anomalous concentration values observed at predose will be identified in the study report and used for the computation of PK parameters. Any other BLQ concentrations will be assigned a value of zero if they precede quantifiable samples in the initial portion of the PK profile. A BLQ value that occurs between quantifiable data points, especially prior to  $C_{max}$ , will be evaluated to determine if an assigned concentration of zero makes sense, or if exclusion of the data is warranted. Following  $C_{max}$ , BLQ values embedded between 2 quantifiable data points will be treated as missing when calculating PK parameters. If a BLQ value occurs at the end of the collection interval (after the last quantifiable concentration), it will be set to missing. If consecutive BLQ concentrations are followed by quantifiable concentrations in the terminal portion of the concentration curve, these quantified values will be excluded from the PK analysis by setting them to missing, unless otherwise warranted by the concentration-time profile. Any concentration values observed at predose will be identified in the study report and used for the computation of AUC. A minimum of 3 postdose serum concentrations is

---

Document:

Author:

Version Number:  
Version Date:

Final Draft  
11APR2019

Template No: CS\_TP\_BS016 Revision 4  
Effective Date: 01Apr2016

Reference: CS\_WI\_BS005

required for the calculation of serum PK parameters, except for  $C_{max}$ ,  $t_{max}$ , and  $MRC_{max}$  on Day -7 (only 1 postdose sample collection).

For the calculation of  $AUC_{0-144}$ , the concentration collected for the 144-hour timepoint and the actual sampling time will be used for calculating the partial area. Samples with time deviations at the 144-hour timepoint will be included for calculating  $AUC_{0-144}$  and the descriptive and inferential statistics. Any subjects with a missing sample at the 144-hour timepoint will have  $AUC_{0-144}$  excluded from the descriptive and inferential analyses.

$C_{max}$ ,  $t_{max}$ ,  $AUC_{0-last}$ , and  $AUC_{0-inf}$  for lurasidone injectable suspension will be the primary PK parameters and all others will be secondary PK parameters.

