6. INVESTIGATIONAL PLAN

6.1. Overall Study Design

This is a single-center, randomized, double-blind, placebo-controlled, inpatient, single ascending dose (SAD) study designed to evaluate the safety, tolerability, and PK of lurasidone injectable suspension in subjects with schizophrenia. This study will determine the minimum intolerable dose (MID), the maximum tolerated dose (MTD) of lurasidone injectable suspension, and characterize the PK profiles of lurasidone metabolites in serum (ID-14283, ID-14326, ID-11614, ID-20219, and ID-20220) and urine (ID-14283, ID-14326, and ID-11614) in this subject population. The potential effects of gender on the PK of lurasidone injectable suspension and its metabolites will also be evaluated when applicable.

A study schematic is presented in Figure 1. Details of the study assessments and other procedures to be performed at each visit are presented in Table 2, Schedule of Assessments, and Section 10, Study Assessments. The maximum duration for study participation for each subject will be up to approximately 96 days. If necessary, subjects may return to the clinic at any time for an unscheduled visit.

Figure 1: Study Schematic

^a Eligible subjects must be washed out/tapered off of their current antipsychotic medications 5 to 6 half-lives prior to Day -8 (may begin as early as Day -19). Subjects are required to be inpatient from Day -12 to Day 15 (for treatment and observation) and Day 29 to Day 33 (for restabilization to previous medications). Subjects may remain inpatient up to Day 33 (at the Investigator's discretion).

Subjects with schizophrenia who provide informed consent to participate in the study will undergo screening procedures and assessments between Days -35 to -13 to determine study eligibility.

b Subjects will receive 2 oral lurasidone 80 mg doses (Days -7 and -6) and be assessed for safety and tolerability for 5 days (Days -5 to -1) and to allow appropriate time to washout of the oral lurasidone dose.

^c Randomization occurs on Day 1. Cohort 1 will receive a single lurasidone injectable suspension dose of 30 mg or a single placebo injection dose; thereafter, single lurasidone injectable suspension doses of 75, 150, 300, and 450 mg may be administered (cohorts 2-5).

^d Subjects will be monitored for safety after the single lurasidone injectable suspension or placebo injection dose until Day 29. Subjects may be discharged on Day 15 at the Investigator's discretion.

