^e Subjects will restart prior medications (including antipsychotics) on Day 29 under observation of clinical site staff.

Eligible subjects will be washed out/tapered off of their current antipsychotic medications over 5 to 6 half-lives prior to Day -8 (may begin Day -19). Subjects will be monitored for safety during tapering/washout. Subjects will be admitted to the clinical site on Day -12 and are required to be inpatient until Day 15.

Subjects will receive oral lurasidone 80 mg tablets on Day -7 and Day -6 (one dose per day), and be monitored for 5 days to ensure the subject is able to tolerate lurasidone (ie, absence of moderate adverse events). Subjects who tolerate dosing with oral lurasidone 80 mg will be eligible for randomization to receive a single lurasidone injectable suspension or placebo injection on Day 1.

Subjects who are discharged after Day 15 will check into the clinical site again on Days 22 and 29 for scheduled assessments. Subjects will follow protocol procedures to remain in-clinic through Day 33 as they restart their prior medications (including antipsychotics), under observation of the Investigator/clinical site staff (ie, restabilization period).

Subjects who remained in-clinic through Day 29 will remain inpatient through Day 33 as they restart their prior medications (including antipsychotics) under observation of the Investigator/clinical site staff (ie, restabilization period).

The restabilization period may be longer and subjects may remain in-clinic, as deemed necessary by the Investigator.

Subjects who discontinue the study prior to Day 29 will undergo assessments scheduled for Day 29 at the time of discontinuation (see Table 2). Subjects who discontinue the study after Day 29 but prior to Day 61 will undergo assessments scheduled for Day 61 at the time of discontinuation (see Table 2).

Subjects who complete the study per protocol will return to the clinic for a follow-up safety assessment on Day 61 (\pm 2).

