**Figure 1: Study Schematic**

a Eligible subjects must be washed out/tapered off of their current antipsychotic medications 5 to 6 half-lives prior to Day -8 (may begin as early as Day -19). Subjects are required to be inpatient from Day -12 to Day 15 (for treatment and observation) and Day 29 to Day 33 (for restabilization to previous medications). Subjects may remain inpatient up to Day 33 (at the Investigator's discretion).

b Subjects will receive 2 oral lurasidone 80 mg doses (Days -7 and -6) and be assessed for safety and tolerability for 5 days (Days -5 to -1) and to allow appropriate time to washout of the oral lurasidone dose.

c Randomization occurs on Day 1. Cohort 1 will receive a single lurasidone injectable suspension dose of 30 mg or a single placebo injection dose; thereafter, single lurasidone injectable suspension doses of 75, 150, 300, and 450 mg may be administered (cohorts 2-5).

d Subjects will be monitored for safety after the single lurasidone injectable suspension or placebo injection dose until Day 29. Subjects may be discharged on Day 15 at the Investigator's discretion.

e Subjects will restart prior medications (including antipsychotics) on Day 29 under observation of clinical site staff.

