# **7. GENERAL CONSIDERATIONS**

## **7.1. REFERENCE START DATE AND STUDY DAY**

Study Day will be calculated from the reference start date and will be used to show start/ stop day of assessments and events.

Reference start date is defined as the day of the injection study drug, (Day 1 is the day of the injection study drug) and will appear in every listing where an assessment date or event date appears.

- If the date of the event is on or after the reference date then:

Study Day = (date of event – reference date) + 1.

- If the date of the event is prior to the reference date then:

Study Day = (date of event – reference date).

In the situation where the event date is partial or missing, Study Day, and any corresponding durations will appear partial or missing in the listings.

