## 17.3. DOSE PROPORTIONALITY

Dose proportionality assessment for lurasidone and metabolites (ID-14283, ID-14326, ID-11614, ID-20219, and ID-20220) for the administered dose range will be conducted using a power model for  $C_{max}$ ,  $AUC_{0\text{-last}}$ , and  $AUC_{0\text{-inf}}$ . The data will be fitted to a linear regression model:

$$\log(Y) = \alpha + \beta \log(X) + \varepsilon$$

where Y is the PK parameter, X is the dose,  $\varepsilon$  is the error term, and 'Log' represents the natural log. The estimate of the intercept and slope ( $\beta$ ), together with its 90% CI, will be presented. Scatter plots of the natural log of  $C_{max}$ ,  $AUC_{0\text{-last}}$ , and  $AUC_{0\text{-inf}}$  versus log dose, along with the fitted regression line, will be presented. Dose proportionality will be assessed based on the inclusion of 1.0 in the CI for slope.

The adequacy of the model will be examined graphically. If the fit of the linear regression model does not seem adequate, then pairwise comparisons between dose groups for lurasidone will be made for  $C_{max}$ ,  $AUC_{0\text{-last}}$ , and  $AUC_{0\text{-inf}}$  using the following one way ANOVA model on dose normalized log-transformed PK parameters with fixed effect for dose group and employing CIs for the difference in mean between dose groups:

$$\log \frac{Y_{ij}}{Dose_i} = \mu + Dose_i + \varepsilon_{ij}$$

where  $Y_{ij}$  is the PK parameter [either  $C_{max}$ ,  $AUC_{0\text{-last}}$ , or  $AUC_{0\text{-inf}}$ ] value for the  $i_{th}$  dose and  $j_{th}$  subject in that dose group,  $Dose_i$  is the  $i_{th}$  dose group, and  $\varepsilon_{ij}$  is the error term. No statistically significant difference between dose group means provides evidence of dose proportionality. From these analyses, for each PK analyte, least-squares (LS) mean for each dose group along with the corresponding 90% CI and LS mean for each pairwise dose group difference along the corresponding 90% CI in log-scale will be obtained. The results will be transformed back to the original scale by exponentiation to provide geometric LS mean for each dose group along with the associated 90% CI and geometric LS mean ratio along with the associated 90% CI for each pairwise ratio of dose groups.

Two additional models to assess dose proportionality will be completed in the same manner as stated above for the following dose ranges, 75 to 450 mg and 150 to 450 mg.

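### SAP 17.2 carries quantifiable Day 1 predose lurasidone uncorrected into the injection PK parameters, with no carry-over rule for the two 80 mg oral doses, so any residual biases the dose-proportionality slope downward

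*SAP*

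**What the plan says.** SAP 17.2 gives the rule twice: "Any quantifiable anomalous concentration values observed at predose will be identified in the study report and used for the computation of PK parameters", and later in the same paragraph "Any concentration values observed at predose will be identified in the study report and used for the computation of AUC". If nothing is measurable, no carry-over enters at time zero: "predose samples that are BLQ or missing will be assigned a numerical value of zero". SAP 17.2.1 starts AUC at the predose time and reads C_max and t_max directly from the observed data. The same section covers the five serum metabolites.

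The oral run-in is the same in every cohort: 80 mg on Day -7 and again on Day -6. The study schematic in Protocol 6.1 says that Days -5 to -1 serve partly "to allow appropriate time to washout of the oral lurasidone dose". Neither document sets a criterion for showing that washout occurred.

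SAP 17.3 fits a log-log power model to C_max, AUC_0-last and AUC_0-inf, for lurasidone and the metabolites. Its criterion is: "Dose proportionality will be assessed based on the inclusion of 1.0 in the CI for slope". It adds models restricted to 75-450 mg and 150-450 mg.

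**The concern.** The oral tablet and the injection deliver the same analyte, so a measurable Day 1 predose level has an obvious possible source that the SAP does not acknowledge. Such a residual would be the same absolute amount on average in every cohort, while the injected dose varies 15-fold (450/30). Adding a constant to a quantity that rises with dose flattens the log-log relationship.

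C_max, AUC_0-last and AUC_0-inf are primary PK parameters, and the proportionality conclusion rests on where the slope interval falls. C_max is the most exposed. Protocol 6.3.2 expects the depot to absorb more slowly than an oral dose, so the 30 mg peak may be low and even a small residual could be large beside it.

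**Working it through.** The plan has no bias or power figure to reproduce, since the sample size is not formally estimated (SAP 4.4).

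**Inputs from the documents**
- Two 80 mg oral doses. Under the study-day rule in SAP 7.1 there is no Day 0, so they fall 168 h and 144 h before injection.
- Injection doses of 30, 75, 150, 300 and 450 mg, with 6 active subjects each.
- A 90% CI for the slope.
- A washout yardstick, set for prior antipsychotics in Protocol 6.1: "over 5 to 6 half-lives prior to Day -8". An interval of 144 h is 6 half-lives at 144/6 = 24 h and 5 half-lives at 144/5 = 28.8 h.

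**Assumptions (not in the documents)**
- Oral terminal half-life h of 24 to 48 h, with mono-exponential decline.
- Oral/IM availability ratio r of 0.1 to 0.5.
- True exposure exactly proportional to dose.
- Between-subject CV of 30% or 50%.

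**AUC.** Observed AUC is proportional to D + c, where c = 80 × r × (2^(-144/h) + 2^(-168/h)) mg. For example, at h = 28.8 h and r = 0.5, c = 40 × (0.03125 + 0.01754) = 1.95 mg. That is 1.95/30 = 6.5% at 30 mg and 1.95/450 = 0.43% at 450 mg. The slope is the least-squares fit of ln(D + c) on ln D.

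| Oral half-life | c at r = 0.5 | AUC rise at 30 / 450 mg | AUC slope, r = 0.1 to 0.5 | Chance CI contains 1, r = 0.5, CV 30% / 50% |
|---|---|---|---|---|
| 24 h | 0.94 mg | 3.1% / 0.2% | 0.998 to 0.990 | 0.894 / 0.898 |
| 28.8 h | 1.95 mg | 6.5% / 0.4% | 0.996 to 0.979 | 0.877 / 0.891 |
| 36 h | 4.07 mg | 13.6% / 0.9% | 0.991 to 0.958 | 0.807 / 0.864 |
| 48 h | 8.54 mg | 28.5% / 1.9% | 0.982 to 0.917 | 0.570 / 0.763 |

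With no bias the last column is 0.90.

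**Precision of the slope.** SE = s / √Sxx, with s = √ln(1 + CV²) and Sxx = 6 × Σ(ln D − mean)² = 28.2. At CV 30%, s = 0.294 and SE = 0.055. The 90% half-width is 1.70 × 0.055 = 0.094. At CV 50% it is 0.151.

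**C_max.** Write observed C_max as D/30 + q, where q is the residual as a fraction of the true 30 mg C_max. For q = 5%, 10%, 20% and 50% the slopes are 0.984, 0.968, 0.940 and 0.866.

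**Check on the actual sampling times.** I superposed the two oral doses and an IM depot (absorption half-life 120 to 300 h, assumed) in a one-compartment model, with linear-up log-down AUC and r = 0.5.
- AUC slopes: 0.99 (24 h), 0.98 (28.8 h), about 0.95 (36 h) and 0.91 (48 h).
- C_max slopes: 0.99, 0.97 to 0.98, 0.86 to 0.95 and 0.69 to 0.88.
- At 36 to 48 h with the slowest depot, the predose value exceeds the injection's own peak, so t_max at 30 mg would be read as 0 h.

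**Restricted-range models.** At h = 48 h and r = 0.5, the AUC slope is 0.917 over 30-450 mg, 0.951 over 75-450 mg and 0.966 over 150-450 mg. At CV 30% the half-width grows from 0.094 to 0.151 and 0.266.

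**After correction.** Subtracting predose × exp(−k t) with the right k returns the slope to 1.000 in this model. Dropping only the time-zero value would not, because the residual also sits in the early post-injection samples.

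**The case against.** The strongest reply is that no residual has been shown to exist. The interval is there for washout, a predose value below the limit of quantification becomes zero, and neither document gives an oral half-life or assay limit. If lurasidone meets the 5 to 6 half-life yardstick, the bias lies well inside the CI half-width of 0.09 to 0.15. Mono-exponential decline also overstates the residual if there is a fast distribution phase. All of this stands, and it limits the point to a missing rule rather than a demonstrated bias.

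Existing text also helps in part. The 75-450 mg and 150-450 mg models drop the most affected cohorts, so an artefact from low doses should show as a trend across models, though with wider intervals. Predose values must be identified in the report, and SAP 17.1.3 plots them. SAP 6.2 allows exclusion of an unreliable profile, but it names no predose trigger, and exclusion would remove subjects from cohorts of six.

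A reader might also infer that carry-over misleads the Safety Review Team. The documents do not support that. The team weighs clinical, laboratory and exposure data together, and a measured concentration is what the subject carries, whatever its source.

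**Conclusion.** The gap is real: the SAP has no rule for oral carry-over, and any quantifiable residual would inflate the lowest dose most and bias the slope downward from its true value. The direction follows from the design. The size cannot be fixed from the documents.

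Under the assumed ratios of 0.1 to 0.5, the full-range slope bias is at most about 0.01 at a 24 h half-life. At 28.8 h it reaches about 0.02 to 0.03 with a ratio of 0.5. It becomes material only at 36 to 48 h with a ratio near 0.5, giving an AUC slope of 0.91 to 0.95 and a C_max slope of 0.69 to 0.95.

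A reader might infer that residual drug is certain to be present, or that the slope will fall below 1 and proportionality will be wrongly rejected. Neither follows. The first needs a half-life and assay limit that are not given. The second also needs a true slope of 1 and the unfavourable end of the assumptions. The calculation is for lurasidone. The same rule covers the metabolites, for which the documents give no half-lives. This is a worthwhile, inexpensive improvement and not a flaw that invalidates the analysis.

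**What to change.** Keep the observed-data analysis as planned and add to SAP 17.2 and 17.3, before unblinding:

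- If any active subject has a Day 1 predose value above 5% of post-injection C_max, repeat C_max, AUC_0-last, AUC_0-inf and the power models, for lurasidone and metabolites, after subtracting predose × exp(−k t).
- Report these results beside the uncorrected ones. Do not conclude non-proportionality if it disappears after correction.
- Take k from the placebo subjects' Day 1 predose and early samples. These subjects took the same oral doses and their samples are already collected, but Protocol 10.3 usually has only a subset measured, so these samples should be assayed.
- Alternatively, take k from the subject's own Day -6 2 h and Day 1 predose samples, stating that a 2 h value may not be terminal-phase and can under-correct. For example, assume a 36 h terminal half-life and an extra 5-fold distribution drop. The fall over 142 h is then 5 × 2^(142/36) = 77-fold, so the two-point half-life is about 23 h and 1 − 22.7/36 = 37% of the residual AUC stays in.

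The 5% trigger is deliberately low and can fire when the 30 mg AUC bias is under 1%. That is tolerable for a sensitivity analysis, and is one reason not to make the correction primary.

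The Day -6 procedure list in Protocol 10.5.3.2 omits the 2 h PK draw that Table 2 note f, Appendix III and SAP 17.1.1 schedule. These must be reconciled.

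The cost is SAP wording, one modelled sensitivity analysis and a few extra placebo assays.

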### 17.2.1. SERUM PARAMETERS AND DERIVATION

The following serum PK parameters will be estimated by noncompartmental methods for lurasidone and metabolites (ID-14283, ID-14326, ID-11614, ID-20219, and ID-20220) using actual elapsed time from dosing on Day 1 following injectable suspension administration unless noted otherwise:

$C_{max}$	Maximum concentration in serum (ng/mL), obtained directly from the observed concentration versus time data (Day -7 and Day 1).
$t_{max}$	Time of maximum concentration (h), obtained directly from the observed concentration versus time data (Day -7 and Day 1).
$C_{last}$	The last postdose quantifiable serum concentration (ng/mL).
$t_{last}$	Time of the last postdose quantifiable serum concentration (h).
$\lambda_z$	Terminal rate constant (1/h), determined by linear regression of the terminal points of the log-linear concentration-time curve. Visual assessment will be used to identify the terminal linear phase of the concentration-time profile.
$t_{1/2}$	Terminal half-life, calculated as $\ln(2)/\lambda_z$ .
$AUC_{0-last}$	Area under the concentration-time curve in serum from time zero (predose) to time of last quantifiable concentration (ng·h/mL), calculated by linear up log down trapezoidal summation.
$AUC_{0-inf}$	Area under the concentration-time curve in serum from time zero (predose) extrapolated to infinite time (ng·h/mL), calculated by linear up log down trapezoidal summation and extrapolated to infinity by addition of the last quantifiable concentration divided by the terminal rate constant: $AUC_{0-last} + C_{last}/\lambda_z$ .

---

Document:

Author:

Version Number:  
Version Date:

Final Draft  
11APR2019

Template No: CS\_TP\_BS016 Revision 4  
Effective Date: 01Apr2016

Reference: CS\_WI\_BS005

